**Statistical Analysis Plan**  
 Sponsor: Selecta Biosciences  
 Protocol No.: SEL-212/302

---

In a supportive analysis, the total number of gout flares by TP3-Day 28 will be analyzed. Missing values of total number of gout flares by TP3-Day 28 will be multiple imputed by using the RPMM method considering tophus status at baseline and treatment group. The total number of gout flares will be analyzed using an ANOVA with treatment and randomization stratum as fixed effects.

### 9.3.3. Additional Secondary Efficacy Endpoints and Analyses

- Percentage of patients who achieve and maintain reduction of sUA < 6 mg/dL for 100% of the time during TP6:

A frequency table of number and percentage of patients who achieve and maintain reduction of sUA < 6 mg/dL for 100% of the time during TP6 will be provided on the ITT population. Each SEL-212 treatment group will be compared versus placebo using the MH estimate and test for common risk difference considering the randomization stratum of tophus presence (yes/no) on the ITT population. In addition, 95% confidence intervals for treatment differences between each SEL-212 treatment group and placebo will be computed.

- Number with pre-dose sUA values < 6 mg/dL during TPs 2-6 for each patient:

A summary table of the mean number of TPs with pre-dose sUA values < 6 mg/dL during TP2 to TP6 will be provided by treatment group on the ITT population. Each SEL-212 treatment group will be compared versus placebo using ANCOVA model with the number of pre-dose values < 6 mg/dL during TPs 2-6 for each patient as dependent variable and treatment group as independent fixed effect variable. 95% confidence intervals for treatment differences between each SEL-212 treatment group and placebo will be presented.

- Anti-pegadricase and anti-uricase antibody formation and levels, pre-treatment for each treatment period in the SEL-212 active treatment arms:

Summary table of pre-treatment values of each variable will be provided by treatment period and by SEL-212 treatment group on the ITT population.

A descriptive summary table of D21 anti-pegadricase and anti-uricase antibody titers, D21 uricase activity values and D21 SUA values at each treatment period, stratified by treatment arm and whether or not the D21 SUA was above or less than or equal to the stopping rule level for that TP (i.e.  $\leq 1$  mg/dL in TP1 and  $\leq 6$  mg/dL in TPs 2-6).

- In patients with tophi at Baseline, the percentage of patients with at least PR (as best response) in overall tophus response evaluation until Day 0 of Treatment Period TP4

Pairwise comparison of each SEL-212 treatment group versus placebo will be performed using the Chi-square test with continuity correction. In addition, 95% confidence intervals for treatment differences between each SEL-212 treatment group and placebo will be computed.

Frequency table of tophaceous patients at baseline with best response in the overall tophus evaluation resulting in at least PR / stable disease progressive disease will be provided by treatment group and period on the ITT population.

This document is confidential.

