7.6.3.2 Phase 2 Studies with SEL-212

7.6.3.2.1 Phase 2 Study SEL-212/201

The Phase 2 study SEL-212/201 was designed as an open-label, ascending multiple-dose study of the combination drug, SEL-212, combined with an open-label, multiple-dose evaluation of SEL-037 (pegadricase) alone in patients with symptomatic gout and elevated blood uric acid. Part A of the study consisted of three 28-day treatment cycles of SEL-212, which was then followed by Part B, which consisted of two 28-day treatment cycles of SEL-037 alone, with a primary objective of assessing the safety, tolerability, PK, PD of SEL-212 (i.e., the combination of SEL-110 and SEL-037). Additional assessments include the ability of SEL-212 to reduce serum uric acid levels and prevent anti-drug antibodies to uricase and pegadricase. Part C of the study consisted of 5 monthly doses of SEL-212.

In Study SEL-212/201 with SEL-212, sUA levels remained consistently below 6 mg/dL in 70% to 89% of evaluable Part A patients administered SEL-212 once monthly for 3 months. The control of sUA occurred in the context of low incidences of infusion reactions, anaphylaxis, and gout flares as well as treatment-emergent adverse events (TEAEs) known to be potentially associated with rapamycin (sirolimus -

Rapamune®). Data support a once monthly dosing regimen. For cohorts 7-12 with SEL-110 doses of 0.1 mg/kg or higher, 46% of evaluable patients had sUA <6 mg/dL at week 20.

In Part C cohorts receiving 5 monthly doses of SEL-212, 61%, 71%, and 67% of eligible patients in Cohorts 13, 15, and 17, respectively, maintained sUA control (sUA, <6 mg/dL) at week 12 without the development of ADAs. All 21 patients in cohorts 13, 15 and 17 who had sUA < 6 mg/dL at week 12, maintained sUA control through the end of treatment period 5 and had sUA < 6 mg/dL at week 20.

The efficacy signal of SEL-212 in SEL-212/201 persists across multiple treatment cycles in all cohorts and through all 5 treatment cycles when SEL-212 is given at each treatment, as demonstrated by dose-dependent reductions in sUA levels below 6 mg/dL and ADA suppression in conjunction with increasing SEL-110 dose levels up to 0.15 mg/kg.

Cohorts 7,11, 13 and 17 represent the dose regimens that will be evaluated in the Phase 3 program (0.1 or 0.15 mg/kg SEL-110 and 0.2 mg/kg SEL-037). Part C cohorts 13, 15, and 17 received 5 once monthly doses of SEL-212, and patients in the proposed Phase 3 program will receive a total of 6 or 12 once monthly doses of SEL-212.

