12.1.8.6 Antibody Assessments

Blood samples will be collected for assessment of antibody development to pegadricase and uricase and for neutralizing antibodies and anti-pegadricase point of service validation. All blood samples for assessment of antibody development are required to be collected prior to study drug dosing. Antibody samples collected after the screening period will be assessed only in patients in active treatment arms.

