**Stopping Rules:**

A patient will be withdrawn from study drug for meeting the following stopping rule:

- sUA level < 2.0 mg/dL, measured 1 hour after the infusion of the second component of study drug is completed during Treatment Period 1

AND

- sUA level > 1.0 mg/dL measured at the Day 21 visit of Treatment Period 1 or sUA level > 6.0 mg/dL at the Day 21 visit of Treatment Periods 2, 3, 4, or 5

Stopping rules will be assessed by an independent, central, unblinded medical monitor.

If withdrawn from study drug, the patient will continue study visits to the end of Treatment Period 6. The window for all Day 21 visits is +2/-1 days.

If a Day 21 visit sUA value drawn within the protocol window is not available, but if a sUA value drawn at an unscheduled visit after the Day 21 window is available prior to dosing that is  $\leq$  1.0 mg/dL during Treatment Period 1 or  $\leq$  6.0 mg/dL during Treatment Periods 2, 3, 4, or 5, the patient will not be required to be withdrawn from study drug and will be eligible to receive their subsequent dose.

If 1) a Day 21 visit sUA value drawn within the protocol window is not available and no subsequent sUA results are available or 2) a Day 21 visit sUA value drawn within the protocol window is not available and a subsequent sUA drawn at an unscheduled visit after the Day 21 window is  $>$  1.0 mg/dL during Treatment Period 1 or  $>$  6.0 mg/dL during Treatment Periods 2, 3, 4, or 5, then the patient will be withdrawn from study drug based on the protocol deviation. If a protocol deviation occurs where a patient is not able to be dosed within the dosing day window (for example in the case of COVID-19 restrictions temporarily preventing dosing) the current treatment period will be extended up to a maximum of 90 days without skipping doses

This document is confidential.

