**TABLE B:**  
**SCHEDULE OF ASSESSMENTS: DOSING, SUA, AND URICASE ACTIVITY DURING THE TREATMENT PHASE**

Assessments	Day Timepoint	Treatment Periods: 1, 2, 3, 4, and 5				Treatment Period 6							
		D0 				D0 				D7 	D14 	D21 	D28 
		0h	~1.5h	~3.5h	~4.5h		0h	~1.5h	~3.5	~4.5h			
Premedicate: Infusion Reaction		X 					X						
Blood Sample Uricase Activity		X 			X 	X	X 			X 	X	X	X
Blood Sample: sUA		X 			X 	X	X 			X 	X	X	X
Study Drug Infusion (Component 1) 		X-----X 					X-----X 						
Study Drug Infusion (Component 2) 			X  -----X					X  -----X					

[figure not shown]
1. Study drug dosing to occur 28 days from the previous dose with a window of -4 days to +3 day of the intended dosing day.
2. Assessments at this visit are permitted to be performed remotely (inclusive of collecting applicable lab draws and assessments per protocol visit windows).
3. Treatment Period 6 only.
4. Premedication to minimize potential infusion reactions: oral antihistamines at 12 ( $\pm$  2) hours and 2 ( $\pm$  1) hours and IV steroids at 1 ( $\pm$  0.5) hours prior to study medication.
5. Obtain sample prior to study drug infusion.
6. Obtain sample 1 hour (+15/-0 min) after completion of infusion of Component 2. If a patient is withdrawn from study drug, the post-dose uricase activity and post-dose sUA samples do not need to be collected.
7. Component 1 will be SEL-110.36 at 0.1 mg/kg for patients randomized to SEL-212A and SEL-110.36 at 0.15 mg/kg for patients randomized to SEL-212B or will be placebo.
8. Before starting infusion with Component 2, a period of up to 30 minutes is permitted after completion of infusion of Component 1.
9. Component 2 will be SEL-037 for patients randomized to either SEL-212A or to SEL-212B or will be placebo for patients randomized to placebo.

This document is confidential.

**TABLE C: DOSING, SERUM URIC ACID, AND URICASE ACTIVITY ASSESSMENT SCHEDULE  
 (TREATMENT PERIODS 1, 2, 3, 4, AND 5)**

**TABLE D: DOSING, SERUM URIC ACID, AND URICASE ACTIVITY ASSESSMENT SCHEDULE  
 (TREATMENT PERIOD 6)**

This document is confidential.

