#### 9.3.4. Exploratory Endpoints

All exploratory endpoints will be summarized on the ITT population.

- Levels of uricase activity in patients receiving SEL-212:

Summaries for each SEL-212 treatment group will be provided by period.

- Effect on monosodium urate crystal deposits and/or total body monosodium urate crystal deposits (imaging patients only):

Frequencies and summaries will be provided by treatment group, and period, if appropriate.

- Levels of inflammatory and tolerogenic biomarkers:

Frequencies and summaries will be provided by treatment group, and period, if appropriate..

- Changes in antibody production (anti-uricase and anti-pegadricase) in patients in the SEL-212 groups:

Summaries for each SEL-212 treatment group will be provided by period.

- Gout flare incidence during Treatment Periods 4-6

A summary table of incidence of gout flares during TPs 4-6 will be presented, based on the ITT population, but including only patients who were still being followed up at the start of TP 4. The incidence is defined as the total number of gout flares a patient experiences between TP4 day 0 and TP6 day 28, divided by the length of observation of the patient in this time period.

An ANCOVA model will be performed with incidence of gout flares as the dependent variable, and treatment and randomization stratum as fixed effect variables. The LSMean difference between

This document is confidential.

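### The Day 21 table of antibodies, uricase activity and sUA has no dosing condition, so from Treatment Period 2 its above-level stratum can mix on-drug loss of control with patients already off drug

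*SAP*

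**What the plan says.** SAP 9.3.3, under the antibody endpoint, specifies "A descriptive summary table of D21 anti-pegadricase and anti-uricase antibody titers, D21 uricase activity values and D21 SUA values at each treatment period", and this is "stratified by treatment arm and whether or not the D21 SUA was above or less than or equal to the stopping rule level". The cut-off is 1 mg/dL in Treatment Period 1 and 6 mg/dL in Periods 2 to 6. Arm and Day 21 sUA are the only stratifiers.

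Under the stopping rules in SAP 3.3, a patient leaves study drug on a Day 21 sUA above the level, for example "sUA level > 1.0 mg/dL measured at the Day 21 visit of Treatment Period 1", provided that the one-hour post-infusion sUA in Period 1 was below 2.0 mg/dL. Leaving drug is not leaving the study: "If withdrawn from study drug, the patient will continue study visits to the end of Treatment Period 6". Protocol 7.1.3 applies this to withdrawal from drug for any reason.

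Sampling continues as well. The footnote to SAP Table B waives only the samples around an infusion: "If a patient is withdrawn from study drug, the post-dose uricase activity and post-dose sUA samples do not need to be collected". Antibody assay depends on arm, not on current dosing (Protocol 12.1.8.6): "Antibody samples collected after the screening period will be assessed only in patients in active treatment arms".

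**The concern.** Protocol 7.6.6 says that antibodies will be correlated with response to SEL-212. The SAP does not state a purpose for the Day 21 table, but it is the one planned display that puts antibody titer, uricase activity and sUA side by side. The other summaries in SAP 9.3.3 and 9.3.4 take antibodies or uricase activity alone, or set antibody status against multiomic markers.

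A reader will use the table to ask whether patients who lose urate control have higher titers and lower enzyme activity. That works if the above-level patients had been dosed three weeks before. If many received no drug in that period, low activity and high sUA follow from the missing infusion whatever the titer, and the titer itself was measured long after the last exposure. The contrast then partly restates who had been stopped.

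**Working it through.** The plan gives no figure for this table, so there is none to reproduce. The check has four steps.

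**1. Who is in each row.** The table text has no dosing condition. Withdrawn patients attend Day 21 visits, their Day 21 sUA and uricase samples are not waived, and their antibody samples are assayed if they are in a SEL-212 arm. Someone stopped on Day 21 of Period 1 is therefore undosed, and still in the table, from Period 2. The Period 1 row has no such patients.

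**2. Time since last dose.** With 28-day dosing, a patient last dosed in period j is 28 × (k − j) + 21 days from that dose at Day 21 of period k. For j = 1 this gives 49, 77, 105, 133 and 161 days at Periods 2 to 6. A patient still on drug is at 21 days.

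**3. Undosed share at the design failure rate.** Inputs: 47 patients per arm (SAP 3.4) and a 45% responder rate (SAP 3.5, Protocol 13.1). Failures per arm = 47 × 0.55 = 25.85. Assume that these are spread evenly over six periods (25.85 / 6 = 4.31 per period), that each is first seen as a Day 21 value above the level and leads to withdrawal, and that withdrawn patients keep attending and stay above the level. The undosed share at period k is then (k − 1) / k.

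| Period | Already off drug | New, on drug | Undosed share |
|---|---|---|---|
| 1 | 0 | 4.3 | 0% |
| 2 | 4.3 | 4.3 | 50% |
| 3 | 8.6 | 4.3 | 67% |
| 4 | 12.9 | 4.3 | 75% |
| 5 | 17.2 | 4.3 | 80% |
| 6 | 21.5 | 4.3 | 83% |

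**4. Undosed share on the Phase 2 pattern.** Protocol 7.6.3.2.1 reports control at week 12 in 61%, 71% and 67% of eligible patients in Cohorts 13, 15 and 17, and then "All 21 patients in cohorts 13, 15 and 17 who had sUA < 6 mg/dL at week 12, maintained sUA control" through week 20.

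- Off drug by Period 4, per arm of 47: 47 × 0.39 = 18.3; 47 × 0.29 = 13.6; 47 × 0.33 = 15.5.
- With no later losses, the above-level stratum in Periods 4 to 6 is 100% undosed.
- Allowing for chance in 0 of 21: the two-sided 95% upper bound is 1 − 0.025^(1/21) = 0.161 over two periods, or 1 − (1 − 0.161)^(1/2) = 0.084 per period.
- New on-drug failures at Period 4 are then 47 × 0.61 × 0.084 = 2.4 or 47 × 0.71 × 0.084 = 2.8. The undosed share is 18.3 / (18.3 + 2.4) = 88% or 13.6 / (13.6 + 2.8) = 83%.
- Carrying the same rate to Period 6 gives 22.9 / (22.9 + 2.0) = 92% or 19.0 / (19.0 + 2.4) = 89%.
- If 5% of off-drug patients sit at or below the level, borrowing the assumed placebo response rate, the lower Period 4 figure becomes 12.9 / (12.9 + 2.8) = 82%.

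**The case against.** The table is descriptive, with no test or interval, and several stronger readings that a reader might draw from it are not supported.

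- *That from Period 4 it compares dosed with undosed patients.* By rule the mixing starts at Period 2; Period 4 comes only from the Phase 2 extrapolation. A first failure in Periods 4 to 6 was dosed and counts as above the level. So does a dosed patient whose one-hour value in Period 1 was 2.0 mg/dL or more, because the rule needs both conditions.
- *That every withdrawn patient returns to the above-level stratum each period.* This is an inference from entry sUA of at least 7 mg/dL and the assumed 5% placebo response. Protocol 7.4.1.1 permits urate-lowering therapy from 60 days after the last dose, while 9.2.1 and 10.5 bar it during the study; those passages must be reconciled. If it is used, some off-drug patients could fall to 6 mg/dL or below, and on these day counts the first Day 21 visit affected is the one at 77 days.
- *That new loss of response cannot be seen.* SAP 10.1 tabulates and plots patients meeting the stopping rules by group and period, and SAP 8.1 plots discontinuations for that reason.
- *That 14 to 18 per arm is a forecast.* The percentages are of eligible patients, with denominators not stated, and Cohort 15 is not among the cohorts that the protocol lists as Phase 3 regimens. On that pattern there is also almost no later loss of control to obscure.
- *That using a stopping level in Period 6 is an error.* The rule ends at Period 5, but the table states its Period 6 cut-off explicitly. This is only a label.

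All of these limits stand. They do not supply the missing dosing condition, and counts of stopped patients do not let a reader separate titers or uricase activity by dosing status.

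**Conclusion.** The point holds as a modest defect in a supportive table. From Period 2 the above-level stratum can combine on-drug loss of control with the absence of a dose for nominally 49 days or more, and the table gives no means of telling them apart. The text of the documents establishes the mixing; they do not fix its size. It runs from about 50% at Period 2 to 83% at Period 6 under evenly spread design failures, and is near total from Period 4 on the Phase 2 pattern. Both estimates assume that off-drug patients keep attending and mostly stay above 6 mg/dL. The first also treats all design failures, whatever their cause, as failures of Day 21 control that lead to withdrawal.

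The loss is limited to the antibody and uricase profile of newly failing patients. The primary and key secondary analyses are untouched.

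**What to change.** In SAP 9.3.3, add dosing status as a stratifier. Within each treatment period and SEL-212 arm, split patients who received study drug on Day 0 of that period by Day 21 sUA above or not above the level, and put previously withdrawn patients in a separate off-drug column.

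In SAP 9.3.4, where "All exploratory endpoints will be summarized on the ITT population", keep the uricase-activity summary as planned. The same on-drug and off-drug split can be added as an option; dropping withdrawn patients from an ITT summary would be a preference, and would select on earlier response.

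The cost is SAP wording and one filter on infusion dates and times that are already recorded (Protocol 9.3). The on-drug, above-level cells will be small: at Period 4, about 4 per arm under the even spread, none at the Phase 2 point estimate, and 2 to 3 at its upper bound. The on-drug rows in later periods will describe only patients who kept control long enough to be dosed again, and a footnote should say so.

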**Statistical Analysis Plan**

Sponsor: Selecta Biosciences

Protocol No.: SEL-212/302

The time until the first tophus reduction (i.e. the first time PR (as best response) is assessed in overall tophus response) will be summarized using descriptive statistics by treatment group for tophaceous patients at baseline in the ITT population.

- Percentage of patients with development of new tophi in the subgroups of tophaceous patients and in non tophaceous patients at baseline during Treatment Periods 1-6:

A frequency table of number and percentage of patients will be provided by treatment group and tophus status at baseline on the ITT population who developed new tophi during the study until Day 28 of TP6, i.e. were classified as PD due to new tophi in the overall tophus response evaluation. Pairwise comparison of each SEL-212 treatment group versus placebo will be performed using the Chi-square test with continuity correction. In addition, 95% confidence intervals for treatment differences between each SEL-212 treatment group and placebo will be computed.

The actual value and the change from baseline of the total number of tophi will be summarized for each scheduled visit by treatment group. Location of tophus, palpation and appearance will be summarized by category, as appropriate, by treatment group for each scheduled visit.

- Change from baseline to Day 28 of TP6 in subscales of Health Assessment Questionnaire (HAQ-DI), in subscales of Short Form Health Survey (SF-36) and in Provider Global Assessment of Disease Activity (PGA)

Summary table of actual values and change from baseline will be provided for all subscales of HAQ-DI, for all subscales of SF-36, the two component scores of SF-36, and the PGA, by period and treatment group. Pairwise comparison of each SEL-212 treatment group versus placebo will be performed using MMRM with the change from baseline in the respective health assessment score as dependent variable and treatment, period, treatment by period interaction, randomization stratum, and baseline value of the respective health assessment as fixed effects. The LSMean difference between each SEL-212 and placebo treatments groups will be presented for TP6, along with its 95% confidence interval, and 2-sided p-values.

HAQ-DI subscales and SF-36 subscales and component scores are described in Sections 9.3.2.5 and 9.3.2.3 of this SAP, respectively. The PGA will be administered to assess the severity of the patient's disease on a scale from 0 (patient feels "very well") to 100 (patient feels "very poor"). Lower scores indicate less severe disease.

- Percentage of Patients with Gout flares:

Frequency table of the number and percentage of patients reporting at least one gout flare in the study until end of Month 6, in the first 3 months, and the next 3 months will be summarized by treatment group on the ITT population.

The number and percentage of patients with at least one life-threatening / at least one severe but no life-threatening / at least one moderate but no severe or life-threatening / only mild gout flares will be presented for each treatment group for all 6 months, but also per 3-month period (first 3 months and next 3 months) on the ITT population.

The percentage of patients with gout flares will be compared between each SEL-212 treatment group versus placebo on the ITT population using the MH estimate and test for common risk difference considering the randomization stratum of tophus presence (yes/no). This analysis will be performed separately for the whole treatment period of 6 months and for the first 3 months after

This document is confidential.

SAP Version: 1.1, 22 Feb 2023

Filing requirements: TMF

**Statistical Analysis Plan**  
 Sponsor: Selecta Biosciences  
 Protocol No.: SEL-212/302

---

start of study treatment. 95% confidence intervals for treatment differences in proportions between each SEL-212 treatment group and placebo will be computed.

- Change from Baseline to Day 28 of TP6 in number of swollen joints:

The number of swollen joints at scheduled visits and the change from baseline will be summarized by treatment group on the ITT population. Pairwise comparison of each SEL-212 treatment group versus placebo will be performed using MMRM with the change from baseline in the number of swollen joints as dependent variable and treatment, period, treatment by period interaction, randomization stratum, and baseline number of swollen joints as fixed effects. The LSMean difference between each SEL-212 and placebo treatment groups will be presented for TP6, along with its 95% confidence interval, and 2-sided p-values.

- Length of time patients are anti-uricase antibody free or before induction of anti-uricase antibody levels above baseline in patients receiving SEL-212:

A summary table will be provided for each SEL-212 treatment group on the ITT population.

- Length of time patients are anti-pegadricase antibody free or before induction of anti-pegadricase antibody levels above baseline in patients receiving SEL-212:

A summary table will be provided for each SEL-212 treatment group on the ITT population.

